#### **10.4.4 Reasons for vaccination discontinuation and early study termination**

The number and percentage of participants who discontinue vaccination and who terminate the study early will be tabulated by reason and treatment arm (Part B).

## 10.5 Analyses prior to end of scheduled follow-up visits

Any analyses conducted prior to the end of the scheduled follow-up visits should not compromise the integrity of the trial in terms of participant retention or safety or immunogenicity endpoint assessments. In particular, early unblinded analyses by treatment assignment require careful consideration and should be made available on a need-to-know basis only.

### 10.5.1 Safety

During the course of the trial, unblinded analyses of safety data will be prepared approximately every 4 months during the main study for review by the SMB. Ad hoc safety reports may also be prepared for SMB review at the request of the HVTN 303 PSRT. The HVTN leadership must approve any other requests for unblinded safety data prior to the end of the scheduled follow-up visits.

## 11 SAFETY TABLES, PARTICIPANT LISTINGS, AND FIGURES

### 11.1 List of Tables

The following tables are included in the SMB reports and FSR for Safety:

### 11.2 List of Tables

The following tables are included in the SMB reports and FSR for Safety:

- Enrollment Report
- Demographics and Study Product Administration Frequencies
- Study Product Administration Errors
- Maximum Local and Systemic Reactogenicity Summaries
- Adverse Events by Treatment – Listed by Body System and Severity – By Decreasing Frequency
- Adverse Events by Preferred Term and Severity – by Decreasing Frequency – Includes Severe, Potentially Life-threatening or Fatal Events only
- Adverse Events by Preferred Term and Severity – by Decreasing Frequency – Includes All Severities
- Adverse Events by Preferred Term and Severity – by Decreasing Frequency – Includes Related Events only
- Adverse Events by Preferred Term and Relationship to Study Product – by Decreasing Frequency – Includes Events of Any Relationship

Additional tables included in the FSR for Safety:

- Social Impact Summary
- End of Study HIV Diagnostic Testing Results (Vaccine-Induced Seropositivity/Reactivity)

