For the 500-mcg groups, 5 of 5 (100.0%) IM recipients and 3 of 5 (60.0%) SC recipients reported at least 1 mild systemic symptom. Mild myalgia was the most frequent symptom, reported by 4 of 5 (80.0%) IM recipients and 1 of 5 (20.0%) SC recipients. Mild malaise was reported by 2 of 5 (40.0%) IM and SC recipients, respectively. Mild headache was reported by 1 of 5 (20.0%) IM recipients and 1 of 5 (20.0%) SC recipients. Mild nausea was reported by 1 of 5 (20.0%) SC recipients. All events resolved within the solicited period. There were no reports of fever or severe systemic solicited reactogenicity symptoms.

Immunogenicity:

Immunogenicity of Trimer 4571 was evaluated by measurement of the trimer-specific antibody in serum samples by Electrochemiluminescence (ECLIA) using a Meso Scale Discovery (MSD) platform at baseline and at 2 weeks after the third product administration. Trimer 4571-specific antibody titers were below the negative cut off values in all groups at baseline. All dose groups displayed detectable antibody responses at 2 weeks after regimen completion (week 22) with the geometric mean AUCs of 674 (95% CI 50-9011), 924 (95% CI 175-4880), 2,529 (95% CI 387-16515), and 1,368 (95% CI 551-3397) for the 100-mcg IM, 100-mcg SC, 500-mcg IM, and 500-mcg SC dose groups, respectively.

Trimer 4571 induced antibodies that were detected by antigen (Ag)/antibody (Ab) Combination HIV testing in participants who confirmed to be HIV negative by polymerase chain reaction (PCR). This reaction is referred to as vaccine-induced seropositivity (VISP). The VRC 018 trial used the VITROS 3600 system Ag/Ab detection assay at the NIH Clinical Center for clinical testing. Samples collected from 7 of 16 participants (43.8%) were reactive in the assay, and therefore seropositive, but participants were confirmed as HIV negative by PCR. Of the 7 participants who were seropositive, 1 was a 100-mcg recipient and 6 were 500-mcg recipients. Six of 7 participants with VISP reverted back to non-reactive on later testing. It is unknown whether the remaining 1 participant (500-mcg recipient) reverted back to non-reactive, as the final follow-up visits were conducted by the telephone, but blood samples were not collected due to the coronavirus disease 2019 (COVID-19) public health emergency stay-at-home orders.

II. NIH-19-I-0069 Phase 1 Study (NCT03878121) [Source: Information provided by Vaccine Research Center (VRC)]

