2.11 Risks and benefits

2.11.1 Risks of the Vaccines:

This is the first study in humans of the investigational vaccines FP8v1-rTTHC and Trimer 6931; therefore, risks are unknown at the time of study start.

The signs and symptoms associated with administration of a similar vaccine, Trimer 4571, are discussed in Section [2.10.1](#).

Most of the risks noted are based on risks of vaccines in general. Potential side effects resulting from intramuscular injections include stinging, discomfort, redness of skin, or mild bruising at vaccine injection site. As with any injection procedure, infection at the site of injection is a possible risk. Signs of infection at the injection site include severe pain, redness, swelling, warmth or drainage.

Participants may exhibit general signs and symptoms associated with administration of the vaccine injection, including fever, chills, rash, aches and pains, nausea, dizziness and fatigue. These side effects will be monitored, but are generally short term, mild to moderate severity and usually do not require treatment.

There may be side effects from the study products, which may be serious or life threatening, that we do not know about yet.

These vaccines are intended to generate antibodies, which may cause a positive or indeterminate HIV antibody result in standard diagnostic tests that may have a negative employment and social impact. HIV PCR will be used to exclude or confirm HIV infection.

The majority of the human population is immune to tetanus toxoid via vaccination. Since the fragment used in FP8v1-rTTHC (FP conjugate) vaccine is not a complete tetanus toxoid, but rather just the heavy chain it is most likely will not be immunogenic. No risks are expected from the tetanus toxoid fragment.

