8.7 Monitoring for HIV infection

Study participants will be tested for HIV infection periodically throughout the study, as indicated in the schedules included in [Appendix A](#), [Appendix B](#), [Appendix C](#) and [Appendix D](#). The Laboratory Program (or approved diagnostic laboratory) will follow the HVTN HIV testing algorithm (see HVTN Laboratory Center MOP), which is able to distinguish vaccine-induced antibody responses from actual HIV infections. Participants will be promptly informed and counseled if they become HIV-infected during the study and will be referred for treatment (see Section [5.2.2](#)).

Study participants will receive regularly scheduled counseling regarding avoidance of HIV infection in accordance with the most recent Centers for Disease Control and Prevention HIV counseling guidelines.

Although the study vaccine will not cause HIV infection, it may induce antibodies detectable by standard HIV infection screening techniques. This is referred to as VISp. The following steps will be taken to protect participants from adverse consequences associated with VISp:

- Participants will be counseled to avoid HIV antibody testing outside of the HVTN CRS during study participation.
- Participants can receive HIV diagnostic testing from the CRS following their last scheduled visit until they are told they do not have VISp.
- Participants with VISp will be periodically offered free-of-charge poststudy HIV diagnostic testing (per the HVTN poststudy HIV testing algorithm) as medically/socially indicated (approximately every 6 months) unless or until HIV antibody testing is no longer standard in clinical settings.
- Unless participants request that their names be removed, the names of all participants in HVTN studies are entered into a secure VISp registry in order to verify that an individual received an HIV vaccine (and therefore has the potential for VISp) and to qualify former participants for post study HIV testing to distinguish between VISp and HIV infection. Information in the VISp registry is not used for research.

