## **4 SAFETY OBJECTIVES AND ENDPOINTS**

*Primary objective 1:*

To evaluate the safety and tolerability of the following regimens in healthy adults:

- Adjuvanted FP conjugate vaccine administered IM at a dose of 25 or 200 mcg,
- Adjuvanted Trimer 6931, administered IM at a dose of 100 or 200 mcg,
- Adjuvanted Trimer 4571 administered IM at 200 mcg, or
- Prime-boost vaccination regimens of FP conjugate, Trimer 4571, and Trimer 6931 vaccines.

*Primary endpoint 1:*

Local and systemic reactogenicity signs and symptoms, laboratory measures of safety, and adverse and serious adverse events.

SAEs, medically attended adverse events (MAAEs), adverse events of special interest (AESIs) and AEs leading to early participant withdrawal or permanent discontinuation which will be collected throughout the study and for 12 months following any receipt of study product. Additionally, all adverse events will be collected for 28 days after any receipt of study vaccination. All safety lab related adverse events will be collected throughout duration of study.

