### **11.3 List of Participant Listings**

These participant listings are included in the SMB reports:

- Discontinuation Status
- Severe or Life-Threatening Local and Systemic Reactogenicities
- Moderate, Severe or Life-threatening Erythema / Induration
- Serious Adverse Events (SAEs)/Expedited Adverse Events (EAEs)
- Severe, Life-Threatening, or Fatal Adverse Events
- Adverse Events of Special Interest (AESI)
- Medically Attended Adverse Events (MAAE)
- Study Product Related Events
- Pregnancies
- HIV Infections

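### The SAP tabulates vaccine-induced seropositivity only from the end-of-study HIV test and plans no any-time or per-visit count, although interim HIV tests are scheduled in every arm

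*SAP*

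**What the plan says.** Protocol 2.11.1 names VISP as a risk: the antibodies "may cause a positive or indeterminate HIV antibody result in standard diagnostic tests that may have a negative employment and social impact". Protocol 8.7 sets out steps to protect participants from its consequences. It also says that the HVTN testing algorithm can separate vaccine-induced antibody from infection.

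On testing, Protocol 8.7 states: "Study participants will be tested for HIV infection periodically throughout the study". Appendices B and D schedule HIV diagnostic tests at several interim visits and at the last visit.

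On reporting, SAP 11.2 lists, for the final safety report only, "End of Study HIV Diagnostic Testing Results (Vaccine-Induced Seropositivity/Reactivity" and, just above it, "Social Impact Summary". SAP 11.3 lists "HIV Infections" among the participant listings for Safety Monitoring Board reports. No other table, listing or figure in SAP section 11 mentions HIV test results.

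On prior experience, Protocol 2.10.1.1 reports from VRC 018: "Samples collected from 7 of 16 participants (43.8%) were reactive in the assay", although PCR confirmed that these participants were HIV negative. It then adds: "Six of 7 participants with VISP reverted back to non-reactive on later testing". The seventh participant's later status is unknown because no blood sample was taken at the final contact.

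**The concern.** VISP can come and go. A table built on one test about a year after the last dose gives the proportion still reactive at exit. It does not give the proportion who were reactive at some point during follow-up, and it says nothing about how long reactivity lasted. The protocol's own prior data show most cases reverting, so the two proportions may differ considerably.

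The in-study period matters by the protocol's own account, because Protocol 8.7 counsels participants against HIV antibody testing elsewhere while they are in the study. At stake is how completely the final safety report describes a named harm of these products, when tests that could inform it are already on the schedule.

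**Working it through.** **1. When HIV tests are scheduled.** The source is the HIV diagnostic test and daily blood volume rows of Protocol Appendix B (Part A) and Appendix D (Part B). Some rows lose a value in the extracted text, so test visits were confirmed by adding up volumes.

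- Part A: Days 84, 168 and 280, then the final visit at Day 364. Check at Day 84: serum 8.5 + PBMC 17 + HIV test 10 = 35.5 mL, as printed.
- Groups 6 and 7: Days 98, 182, 266 and 350, then Day 392. Check for Group 6 at Day 98: 3 + 4 + 8.5 + 42.5 + 10 = 68 mL, as printed.
- Group 8: Days 70, 154, 238 and 322, then Day 392. Check at Day 70: 3 + 4 + 8.5 + 42.5 + 10 = 68 mL. Check at Day 322: 204 + 10 = 214 mL. Both are as printed.

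That is three interim tests in Part A and four in each Part B group. The HIV test volume is 10 mL at interim visits and 20 mL at the final visit.

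**2. Distance of the final test from the last dose.** Part A: 364 days. Part B with one dose: 392 days. Part B with a second dose at the target Day 28: 392 − 28 = 364 days.

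**3. The prior rate.** 7/16 = 43.75%, which reproduces the protocol's 43.8%. Intervals use the score method that the protocol names:

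[p + z²/(2n) ± z·√(p(1−p)/n + z²/(4n²))] / (1 + z²/n), with z = 1.96.

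The same code reproduces these entries in Protocol Tables 6-2 and 6-3: 0/3 upper limit 56.1, 0/9 upper limit 29.9, 9/9 lower limit 70.1, and 3/13 [8.2, 50.3]. It gives:

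- ever reactive, 7/16: 43.8% (23.1 to 66.8);
- reverted among those reactive, 6/7: 85.7% (48.7 to 97.4; exact interval 42.1 to 99.6).

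By dose, the reactive participants were 1 of 6 at 100 mcg (16.7%) and 6 of 10 at 500 mcg (60.0%).

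**4. Illustration for this trial (an assumption, not a document figure).** Trimer recipients are Groups 3, 4, 5, 6 and 8: 3 + 3 + 3 + 10 + 9 = 28.

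| Assumed ever-reactive rate | Ever reactive among 28 | Not shown at end if 6/7 revert | Not shown if 48.7% revert |
|---|---|---|---|
| 1/6 | 28 × 1/6 = 4.7 | 4.7 × 6/7 = 4.0 | 2.3 |
| 6/10 | 28 × 6/10 = 16.8 | 16.8 × 6/7 = 14.4 | 8.2 |

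Six of the 28 (Groups 3 and 4) received Trimer 6931, which had no prior human data. The other 44 − 28 = 16 participants (Groups 1, 2 and 7) received FP conjugate only, and the documents give no prior VISP rate for it.

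**5. Whether another output fills the gap.** The infections listing is titled for infections, not for reactive but uninfected participants, and it is listed for board reports. The social impact table covers consequences, not how many participants became reactive. General adverse event collection runs for 28 days after each vaccination (Protocol 9.1). The first HIV test is at Day 70 or later, at least 70 − 28 = 42 days after a second dose given on the target day. Protocol 9.1 does not class a reactive test in an uninfected participant as an adverse event.

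**The case against.** The strongest case on the other side has five parts.

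- **Size.** A reader might infer that the final report would miss most participants who ever had VISP, or would understate it seven-fold (7 of 16 against at most 1 of 16). The documents do not support either as a prediction. Both rest on 7 cases, and the lower score limit for reversion (48.7%) is below half. VRC 018 gave up to three doses with alum at 100 or 500 mcg and used one named assay, and no reversion times are reported. Here 33 participants had one dose and 11 had two, with Adjuplex and under the HVTN algorithm. This objection stands, so the claim must be conditional.
- **Data.** The documents do not say that each interim test yields an antibody result usable for VISP. The larger final draw may mean a different panel. This stands, and the fix must allow for it.
- **Meaning of any-time.** With the first test at Day 70 to 98, earlier transient reactivity goes unseen, so an any-time count is itself a lower bound. This also stands. The count is still never smaller than the end-of-study count alone.
- **Purpose.** Post-study testing is offered to participants with VISP (Protocol 8.7), so status at exit is worth reporting. True, and a reason to keep the table, but not a reason to omit the rest.
- **Priority.** VISP is not named in primary endpoint 1 ("Local and systemic reactogenicity signs and symptoms, laboratory measures of safety, and adverse and serious adverse events"), and SAP 11.2 gives table titles, not shells, so the finished table might contain more than its title promises. That lowers the urgency. As written, though, nothing commits the report to interim results.

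**Conclusion.** The gap is real: as written, the SAP reports VISP at one late time point and commits to no any-time, per-visit or duration summary, while interim HIV tests are scheduled in every arm. If any participant reverts before the last visit, the end-of-study count falls below the number ever reactive. If reversion resembles VRC 018, the shortfall could be substantial.

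How large it would be after one or two Adjuplex-adjuvanted doses is unknown. The range of about 4 to 14 participants not shown, out of about 5 to 17 ever reactive, assumes that VRC 018's dose-specific rates and its 6/7 reversion carry over to all 28 trimer recipients, including the six who received Trimer 6931. It shows scale and is not a forecast.

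This is a worthwhile, low-cost improvement to reporting. It does not question the conduct of testing or any clinical rule.

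**What to change.** In SAP 11.2, keep the end-of-study table and add, by arm:

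1. the number and percentage of participants with a reactive result, confirmed HIV-uninfected, at any scheduled post-vaccination test, with a 95% score interval;
2. the number reactive at each scheduled test, with the number tested.

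Use interim antibody results where the testing algorithm produced them, and say so where it did not. Footnote three things: the test days by group; any assay difference between interim and final tests; and that any-time reactivity is a lower bound because the first test falls at Day 70 to 98.

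The cost is one extended table and a retrieval of interim HIV diagnostic results, which may have to come from the testing laboratory if they are not in the study database. No visit, sample or procedure changes. The remaining limitation is that test days differ between groups, so any-time rates are not strictly comparable across arms. The first footnote makes that visible.

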### **11.3 List of Participant Listings**

These participant listings are included in the SMB reports:

- Discontinuation Status
- Severe or Life-Threatening Local and Systemic Reactogenicities
- Moderate, Severe or Life-threatening Erythema / Induration
- Serious Adverse Events (SAEs)/Expedited Adverse Events (EAEs)
- Severe, Life-Threatening, or Fatal Adverse Events
- Adverse Events of Special Interest (AESI)
- Medically Attended Adverse Events (MAAE)
- Study Product Related Events
- Pregnancies
- HIV Infections

### **11.4 List of Figures**

These graphs are included in the SMB reports and FSR for Safety:

- Maximum Local Reactogenicities
- Maximum Systemic Reactogenicities
- Boxplots for Laboratory Measures

